7.6.2. NIR Procedures

All participants will attend 16 NIR stimulation sessions in the laboratory. During each session, the participant will be seated comfortably in a chair. The LED clusters will be positioned on the scalp and the intranasal units will be positioned in the nostrils. Approximately 40 minutes of stimulation will occur, broken into two 20 minutes segments. Intranasal stimulation will occur for 25-50 minutes.

During the actual stimulation period, ***participants will view nature documentaries*** (BBC Life Nature documentary series; Gunton, 2009; One Planet, Seven Worlds series, Keeling, 2019) that are shown on a monitor during the duration of stimulation. This is being done in order to standardize cognitive engagement and control for differences in cognitive activity during stimulation. This will also be done to reduce conversation between the examiners and the participant during the period of stimulation, which could differ between participants. Episodes of the BBC Life Nature Documentary will be presented in the same order for each participant, with a different episode played at each stimulation session. The episodes include the following:

1. “Challenges of Life”: This episode is the series opener and features stories of animal behavior such as feeding, hunting, and courting from around the world. Animals featured include killer whales, poison-dart frogs, and penguins.
2. “Mammals”: This episode features the life of mammals from around the globe. Stories feature animals such as reindeer, polar bears, African elephants, and humpback whales.
3. “Birds”: This episode features stories of birds from across the globe. Nesting, parenting, and migratory behaviors are described from animals such as humming birds, pelicans, grouses, and bowerbirds.
4. “Creatures of the Deep”: This episode features an exploration of life in the deep ocean. Deep-sea creatures such as jellyfish, spider crabs, sea urchins, octopus, and coral reefs are described.
5. “Plants”: This episode utilized time-lapse photography and videography to explore the behavior of plants. Featured plants include Venus flytraps, sundews, milkweeds, dragons blood trees and mangrove trees.
6. “Primates”: This episode features stories of primates and the attributes that have made them a highly successful group of mammals. Animals featured include lemurs, gibbons, orangutans, and macaques.
7. “Fish”: This episode features the countless number of fish that fill the seas and almost all other waters on the blue planet.
8. “Reptiles & Amphibians”: This episode features reptilians, which survive from the age of the Saurians. Examples include lizards like the giant Komodo dragon, the feared crocodilian

hunters, color-changing chameleons and snake species fitted for most (warm) ecosystems. Featured amphibians include numerous specialized (tree) frogs and toads. Both groups are cold-blooded, hence vulnerable while warming up

9. "Insects": This episode feature insects, which outnumber all other species on earth. Their immense variety effect adaptation to an extreme range of ecological conditions. Nearly 60,000 fly species cover about the globe.
10. "Hunters and the Hunted": This episode features the struggle of life which is often based on eat and/or be eaten. Therefore, evolutionary success is based on struggle for skills to survive as prey or hunter. Mammals are particularly successful worldwide because the add to anatomical adaptation an intelligence allowing quick and greatly diverse strategies to find preys, shelter, fight (back)
- 11-16. "One Planet-Seven Worlds": This BBC series consists of one hour episodes, each involving the wildlife and unique landscapes/geography of each continent, emphasizing how the development of each continent shaped the diversity of animal life.

Questionnaires: Following the NIR stimulation, participants will complete the POMS short form and will be queried for adverse events (using the Adverse Events log). Completion of these questionnaires will take place at the end of each session.

7.6.3. SHAM NIR Condition and Blinding

Participants in the sham group will undergo identical informed consent, screening, pre-post testing, and NIR intervention sessions. The only difference is that "sham" MedX and Vielight devices will be used. These are identical in all respects to real devices except that they do not deliver NIR. The research assistant administering the lab stimulation session will be aware of the participant's treatment status, but will have no role in pre- or post-intervention assessments. The research assistant involved in testing and neuroimaging acquisition will be blinded to the treatment status of the participant.

Shown below is an overview of the temporal overview of the procedures.

Table 2: Overview of Procedures and Protocol

Measures	Pre-screen	Screening	Base-line	Intervention	Follow-up	3-month
Telephone Screening	X					
Inclusion / Exclusion	X	X				
Informed Consent		X				
Contact Information		X				
Demographic Info		X				
Medical & Psychiatric History		X				
Medications/Magellan		X				
MoCA		X				
NACC Neuropsych Battery		X				
Mental Health Screen V.3		X				

Charleson		X				
WTAR		X				
Vision Screen		X				
Functional Activity Questionnaire (FAQ)		X			X	X
Clinical Dementia Rating		X				
Cognitive Change Index (CCI) – participant & informant		X			X	X
Blood Draw			X		X	
MRI Screener	X	X	X		X	
MRI			X		X	
Skin type Questionnaire			X			
Expectation Questionnaire			X			
ARENA			X		X	X
NIH Examiner (Working Memory and other Examiner subtests)			X		X	X
MST			X		X	X
Rey AVLT			X		X	X
Verbal Fluency			X		X	X
Stroop			X		X	X
Trail Making Test		X			X	X
Logical Memory Stories			X		X	X
Brief Visuospatial Memory Test-Rev			X		X	X
Emotion Module - NIH Toolbox			X		X	X
BDI-II			X		X	X
STAI			X		X	X
Apathy Scale			X		X	X
Pittsburgh Sleep Inventory			X		X	X
Pain Scale			X		X	X
Fatigue Severity Scale			X		X	X
10 Meter Walk Test			X		X	X
POMS			X	X	X	X
Cal-Cap			X		X	X
Adverse Events Log			X	X	X	X
Daily Journal (participant)				X		

NIR Sensation Stimulation Questionnaire				X		
Placebo Control Quest					X	X
Followup Questionnaire					X	X
3-mo Followup Medical					X	X

MoCA=Montreal Cognitive Assessment; NACC=National Alzheimer's Coordinating Center; Charlson = Charlson Comorbidity Index; WTAR=Wechsler Test of Adult Reading; Skin type Questionnaire =Fitzpatrick Skin-Type Questionnaire; MST=Mneumonic Similarity Test; Rey AVLT = Rey Auditory Verbal Learning Test;; CALCAP = California Computerized Assessment Package; BDI-II=Beck Depression Inventory, 2nd edition; STAI=State Trait Anxiety Inventory; POMS=Profile of Mood States, Short Form; Daily journal = completed by participant for recording time of daily intranasal treatment.

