The proposed multi-site collaborative project brings together research teams at the University of Florida (UF) and University of Arizona (UA) to test a novel, relatively low cost, low risk, and potentially high impact therapeutic intervention in older adults who are at increased risk for Alzheimer's disease. The intervention involves transcranial and intranasal delivery of near infrared (NIR) light via light emitting diodes, aka *photobiomodulation*. Prior research in cellular and animal models suggest that red and infrared light are neuroprotective and thought to improve mitochondrial function by promoting increased production of intracellular ATP. Transgenic mouse models of Alzheimer's disease demonstrate reduced beta-amyloid and neurofibrillary tangles in response to transcranial NIR versus sham stimulation. Preliminary human studies have also shown promising behavioral findings in young adults and those with TBI, aphasia, and Alzheimer's disease. From our team, pilot phosphorous magnetic resonance spectroscopy (31P MRS) and cognitive data in older adults support this mechanism of action and provide compelling evidence for a Phase II clinical trial. To more fully determine whether this novel stimulation approach has potential for enhancing cognition in cognitively normal but "at risk" individuals for Alzheimer's disease, we plan to conduct a multi-site double blinded randomized sham-controlled Phase II clinical trial. Our overall hypothesis is that exposure to NIR stimulation will have beneficial effects on brain health via influence on mitochondrial function as measured by changes in 31P MRS-based markers of ATP, neural network changes in functional connectivity (rs-fMRI), and improved cognitive performance. To test this hypothesis, we plan to randomize 168 older adults with subjective cognitive complaints, and a first-degree family history of Alzheimer's disease to sham or real treatment groups and evaluate neuroimaging and cognitive outcome measures, before and after a 12-week intervention involving transcranial and intranasal NIR-PBM. The protocol will involve "lab" and "home" sessions, and a 3 month post-intervention follow-up. This trial will determine: 1) whether NIR stimulation, relative to sham, improves performance on memory and executive tasks sensitive to hippocampal and frontal brain function in older adults with increased risk for Alzheimer's disease; 2) whether NIR stimulation, relative to sham, enhances brain function and connectivity measured by changes in MRS phosphorous ATP and resting state functional connectivity; and 3) how differences in demographic, neuroimaging, and Alzheimer-related risk factors influence the brain response to NIR stimulation versus sham in older adults with increased risk for Alzheimer's disease. Results will provide key insights into whether this novel NIR intervention can enhance cognition in older adults with increased risk for Alzheimer's disease and will provide the necessary data for a future Phase III randomized clinical trial.

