This is a blinded sham-controlled parallel group multi-site clinical trial where nondemented older adults will be randomized to active or sham treatment groups. The intervention phase will extend over 12 weeks and includes transcranial and intranasal stimulation that has “lab” and “home” components. The lab component includes weekly transcranial + intranasal NIR-PBM sessions, whereas the ‘at home’ protocol involves daily intranasal stimulation. The devices used to deliver “real” and “sham” stimulation are identical in all respects to that of our pilot study. The use of a sham design controls for the effects of placebo, activation, and practice.

Our participants will include cognitively unimpaired individuals with “**subjective**” cognitive complaints and a **family history of Alzheimer’s disease** (first degree relatives). We have selected these criteria based on a growing literature that: a) subjective cognitive decline (SCD) is linked to increased AD biomarker abnormalities and increased risk for progressing to MCI and dementia (Saykin et al., 2005; Jessen et al., 2014; Kielb et al., 2017; Kryscio et al., 2014; Colijn et al., 2015; Lista et al., 2015; Contreras et al., 2017; Risacher et al., 2015; Swinford et al., 2018); and b) SCD combined with a family history of Alzheimer’s disease may further heighten AD risk, with findings of resting state patterns that mirror early AD (Verfaellie et al., 2018). We expect that these additive risk factors result in greater vulnerability for cognitive decline, representing an ‘early’ preclinical AD group who would benefit from intervention.

Participants will be tested at 3 primary time points: 1) pre-intervention; 2) immediately post-intervention; and 3) three months later. At each time point, we will obtain cognitive (memory,

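### Staff who run the lab sessions know the arm, with no reason given, which leaves in-session adverse-event data and participant expectations less protected than they need be

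*Protocol*

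**What the plan says.** The project summary at the start of the Protocol calls the study a "multi-site double blinded randomized sham-controlled Phase II clinical trial". Section 7.1 is less specific: "This is a blinded sham-controlled parallel group multi-site clinical trial". Neither says which roles are blind.

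Section 7.6.3 does. Of the sham devices it says "These are identical in all respects to real devices except that they do not deliver NIR". It then says "The research assistant administering the lab stimulation session will be aware of the participant's treatment status", and limits that person's part in the trial: "but will have no role in pre- or post-intervention assessments". Outcome staff are treated differently: "The research assistant involved in testing and neuroimaging acquisition will be blinded to the treatment status of the participant". Section 8.2a likewise keeps assignments from those who administer and score the baseline and post-intervention cognitive and mood data.

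After stimulation, according to 7.6.2, "participants will complete the POMS short form and will be queried for adverse events (using the Adverse Events log", and this happens at the close of every session. Section 7.5.4c describes the log as open-ended and covering severity, duration and, where known, a possible link to the intervention. Section 11 has site safety officers complete evaluation forms for events of sufficient concern. It does not say whether they are blind to arm.

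**The concern.** If real and sham units cannot be told apart except by the light they deliver, an operator could run the session without knowing the arm. The Protocol gives no reason for telling the operator.

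Two things are at stake. The first is direct. An open-ended query about symptoms, their severity and their possible link to treatment depends on how it is asked, how far it is followed up and how the answer is written down. Someone who knows the arm may do each of these differently for active and sham participants, without intending to.

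The second is indirect. An operator who knows the arm and sees the participant repeatedly may give cues that change expectations, and the participant carries those into a blinded assessment. The Protocol itself treats expectation as a live issue: Section 8.4 names placebo effects on cognition as a limitation, and Section 15 allows that some improvement may come from expectation alone.

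**Working it through.** No power or sample-size figure depends on this point. The check is a count of exposure and a comparison of the relevant sections.

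**Number of sessions.** Section 7.6.1 schedules three lab sessions a week in Weeks 1 and 2 and one a week in Weeks 3 to 12. That gives 3 × 2 + 1 × 10 = 16, matching the Protocol's stated 16.

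**Share of adverse-event logs taken in those sessions.** Table 2 schedules the log at baseline, during the intervention, at follow-up and at 3 months; 7.6.2 makes the intervention entry one per session.
- All scheduled completions: 1 + 16 + 1 + 1 = 19, of which 16/19 = 84% are in-session.
- Leaving out baseline, which precedes any stimulation: 16/18 = 89%.
- Across 168 participants with full attendance: 168 × 16 = 2,688 in-session logs, or 84 × 16 = 1,344 per arm.

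**Time in sessions.** Section 7.6.1 gives about 1.5 h per session, including 40 minutes of stimulation.
- Total session time: 16 × 1.5 h = 24 h.
- Stimulation with documentaries playing: 16 × 40 min = 640 min, about 10.7 h.
- Remainder (set-up, repositioning, questionnaires): 24 − 10.7 = about 13.3 h.

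The 13.3 h is session time not covered by the documentaries. It is not a measure of conversation.

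**Who is blind to what.**

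| Data or role | Blinding stated | Where |
|---|---|---|
| Cognitive testing and imaging acquisition | Blind | 7.6.3, 8.2a |
| Lab-session operator | Not blind | 7.6.3 |
| In-session POMS | Self-report; person handing it out not named | 7.5.3b, 7.6.2 |
| In-session adverse-event log | Person asking not named | 7.5.4c, 7.6.2 |
| Site safety officers | Not stated | 11 |

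**How the log is completed.** Section 7.6.2 has participants being queried, whereas Section 11 has them completing adverse-event questionnaires. These need reconciling, because the two methods differ in how far an informed operator can influence the record.

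**Could the operator be kept blind?** Section 7.6 says each LED cluster holds 52 near-infrared diodes and 9 visible red ones. The documents do not say whether the red diodes light up in the sham units. If they do not, an operator placing and moving the clusters could tell the arm whatever the label says.

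**Role separation.** Section 14 uses the title study coordinator both for the person in the cognitive testing offices and for the person applying the diodes. Different people may hold that title, but the wording should be reconciled with 7.6.3.

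**The case against.** The strongest reply is that the plan discloses the unblinded operator and protects what matters most. The primary outcome and all three secondary outcomes lie outside that person's role. Documentaries are shown in a fixed order, partly to limit conversation (7.6.2). About 10% of participants are asked to be videotaped in a baseline and an intervention session as a check on standard conduct (7.7). Participants are asked afterwards which arm they think they had (7.5.4d). The POMS is self-reported, and the SAP plans no analysis of it.

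Most of this stands, and it rules out several stronger readings that a reader might infer:
- That the unblinded assistant collects ARENA or the secondary outcomes. Section 7.6.3 says the reverse.
- That the in-session logs are the only safety data. The log is also scheduled at baseline, follow-up and 3 months.
- That each participant has 24 h of interaction with unblinded staff. That is total session length, and about 10.7 h of it is documentary viewing.
- That the unblinded operator personally asks the adverse-event questions. This is likely, but no section says it.
- That the double-blind label is false. It can mean participant plus outcome assessor, which is the structure described, and in the supplied text only the project summary applies it to this trial. The label is imprecise.

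The safeguards still leave a gap. Blinded testers prevent biased scoring, but not a change in what participants expect. The documentaries cover stimulation only, not set-up or the closing questionnaires. The arm-guess form could detect unblinding, but the SAP plans no analysis of it. None of these measures covers the in-session adverse-event query.

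**Conclusion.** The point holds as a design weakness that is cheap to reduce. Session staff know the arm without a stated reason, and most scheduled adverse-event logs (16 of 19 per participant) are taken in the sessions they run. For ARENA and the secondary outcomes the risk is indirect, through participant expectation. For in-session adverse events it is more direct, because the log asks for severity and possible relatedness and no one is named as a blinded collector or judge.

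The size and direction of any bias cannot be computed from the documents. The conclusion rests on two assumptions: that the operator takes part in the in-session query, or is at least present for it, and that informed staff can influence open-ended answers. If a blinded person already collects the log, or participants already complete it alone, only the expectation route and the wording of the label remain. Changing the label alone would be a clarification; the improvement lies in the handling of devices and adverse events.

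**What to change.** 1. Have the data management group (Section 12) issue number-coded consoles and intranasal units, with the key held away from session staff, so that operators are not told the arm. First confirm that the sham units' visible red diodes do not reveal it.
2. Whether or not step 1 is possible, have participants complete the in-session adverse-event log themselves, as they already do the POMS, and have the existing site safety officers judge relatedness blind to arm. Align 7.5.4c, 7.6.2 and Section 11 on who completes the log. Section 11's review after each session can stay as it is.
3. If operators must stay unblinded, give the reason in 7.6.3 and describe the trial in the project summary as participant- and outcome-assessor-blinded.

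The cost is labels, a code list, some safety-officer time and a few sentences of text. Device logistics become slightly harder. On the documents' description no new staff are needed, and sample size, stimulation and visit schedule do not change. If sessions are already complete, which the documents do not show, the trial report can still state which roles were blind and who collected the in-session data.

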7.7 Videotaping

A random subset of approximately 10% of the participants taking part in the intervention will be asked to have a baseline session and an intervention session video and audio taped. These videos or photos will be used for “quality” control. We want to insure that our research team is conducting the testing and the intervention in a standard manner. These videos or photos will be reviewed by experts at the University of Florida to provide feedback to the research team. Agreeing to be video and audiotaped is not a requirement for study participation.

7.8 Compensation

Participants will be compensated up to \$500 for completing the study. The distribution of payment is as follows:

Completion of Baseline, MRI, and Blood Draw	\$50
Completion of Intervention, post-MRI and follow-up, return of intranasal 810	\$350
Completion of 3 month Follow-up	\$100

8. Outcome and Statistical Approaches

8.1. Outcome Measures

Change in performance on cognitive and imaging parameters (functional connectivity, MRS ATP markers) before and after intervention, relative to the sham control group. Intervention changes must exceed the effects of practice based on the sham control group.

As shown, the protocol as a whole has one primary outcome (ARENA, Aim 1) and three secondary outcomes (*Working Memory*-Aim 1, *31-P MRS ATP*- Aim 2, *rs-fMRI* - Aim 2).

STUDY MEASURES AND OUTCOMES				
Measures	ASSESSMENT SCHEDULE			
	Baseline	During Intervention	Post Intervention	3-Month Followup
Outcome Measures				
Primary Outcome				
ARENA: Aim 1	X		X	X
Secondary Outcomes				
Working Memory: Aim 1	X		X	X
31-P MRS ATP: Aim 2	X		X	
rs-fMRI: Aim 2	X		X	
Exploratory Outcomes				
Verbal Fluency	X		X	X
Mnemonic Similarity (memory)	X		X	X
Auditory Verbal Learning Test	X		X	X
Stroop Color Word	X		X	X
Other Imaging	X		X	
Other Cognitive	X		X	X
Measures of Potential Mediators, Moderators, and Covariates				
Genotype for APOE-e4 status	X			
AD Biomarkers & other	X		X	
Vascular comorbidities	X			
Fitzpatrick Skin Type Questionnaire	X			
Processing Speed (CalCap-RT)	X		X	X
Mood (NIH Toolbox Emotion)				
Negative Affect	X		X	X
Subjective Wellbeing	X		X	X
Other Imaging variables				
Other Measures				
Daily Diary Home Log				
Profile of Mood States	X	X	X	X
Adverse Event	X	X	X	X
Fidelity				
Session Completion	X	X	X	X
Expectation Questionnaire	X			
Placebo Control & F/U Questionnaire			X	X

Aim 1 examines memory and executive function.

- Changes in pre-post scores on ARENA, a human Morris Water Maze analog sensitive to hippocampal function (Primary outcome)
- Changes in pre-post scores on Working Memory subtests from NIH Examiner (Secondary outcome).
- Changes in pre-post treatment scores on Verbal Fluency (NIH Examiner), the Mnemonic Similarity Task, Rey Auditory Verbal Learning Test, Stroop, and traditional neuropsychological measures of executive function (Exploratory outcomes).

Aim 2 examines neuroimaging changes

- Changes in frontal and temporal lobe MRS, including markers of ATP function, and structural imaging variables (Secondary outcome).
- Changes in frontal and medial temporal lobe mediated patterns of resting state functional connectivity (Secondary outcome).

Aim 3 examines potential mediators and moderators of treatment response, including demographic and other variables.

8.2. Randomization and Statistical Methods

8.2a. Randomization

Participants will be independently assigned to Sham and Active groups on a 1:1 ratio. Randomization will be stratified according to age and MoCA scores so as to prevent different average ages or cognitive status scores between the treatment groups (Active, Sham). Treatment assignment will be pseudorandomized in order to have comparable distributions of age and cognitive screening scores across Sham and Treatment interventions. Procedures will be followed so that group assignments are not available to individuals administering and scoring baseline/pre-intervention and post-intervention cognitive/mood data.

8.2b. Missingness and Intent to Treat

All data will be checked for missingness, out-of-range values, and distributional form (i.e., normality, homogeneity of variance). Decisions regarding use of parametric vs. nonparametric statistics will be based on the results of those analyses. Standard summary statistics will be provided for pre- and post-stimulation. Intent to treat analysis will be used to reduce selective attrition bias; participants who are unwilling/unable to continue with intervention will be encouraged to attend the post intervention testing, if possible. Thus, statistical analyses will be performed on two data sets: 1) on all subjects who were successfully screened, randomized and able to participate in at least 1 week of the assigned intervention, regardless of study completion (intention-to-treat analysis); and 2) on subjects who were successfully screened, randomized and able to complete at least 80% of the treatment assignment.

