7.2 Participants

Participants will include 168 older adults with **subjective cognitive complaints** and a first degree family history of Alzheimer's disease. Study participants will be randomized to Active or Sham groups using a 1:1 randomization scheme, stratified by age, education, and gender. We hope to recruit equal numbers of men and women. Half the participants will be enrolled at the University of Florida and half at the University of Arizona. Because each participant will have an informant, this means we will need 336 individuals to sign consent forms (i.e., 168 X 2 [participant plus informant]). Due to estimated potential screen failures (up to 350) and drop outs (i.e., 100), we plan to consent up to 768 individuals who meet inclusion-exclusion criteria. One half the participants will be enrolled at the University of Florida and ½ at the University of Arizona).

Inclusion Criteria

- Age 65-89 years, at least 8th grade education, community dwelling
- Subjective report of cognitive complaints with scores ≥ 16 on the **Cognitive Change Index** (CCI-20), a validated scale of subjective cognitive decline (Saykin et al., 2013).
- No evidence of dementia or mild cognitive impairment based on cognitive screening (e.g., Montreal Cognitive Assessment (MoCA) score is within normal limits for age, education and sex.)
- No psychometric evidence of cognitive impairment based on performance on the Neuropsychological Battery from the National Alzheimer's Coordinating Center Unified Data Set (NACC-UDS), version 3 (Weintraub et al., 2018)
- Reading at $\geq 8^{\text{th}}$ grade level based on the reading subtest of the Wechsler Test of Adult Reading (WTAR).
- Global Clinic Dementia Rating (CDR) score must be 0 (Hughes et al.)
- Family history of dementia/probable Alzheimer's disease in first degree relative (parents, children, siblings)
- Willingness to be randomized to Sham or Active Intervention
- Can devote 12 weeks to the intervention with additional time for pre and post testing
- Normal functional behavior in terms of daily activities, based on the Functional Activities Questionnaire from the NACC-UDS
- Able to perform cognitive and emotion measures on a computer
- Availability of an informant (family member, colleague, friend) to provide information about activities of daily living and cognitive complaints (see Molinueva et al., 2017).

[figure not shown]
Exclusion Criteria

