We plan to have a **Data Safety Monitoring Board (DSMB)** who will consist of experts in cognitive interventions, clinical trials and neuroimaging. The committee will meet every six months via telephone, Skype, Zoom, or other format. Initially, the DSMB will advise NIH staff and MPI's on design and protocol changes, the analysis plan, and planned publications. The DSMB will monitor site performance through semi-annual reports from the research team.

12. Data Management Plan

Data will be kept in a password protected encrypted database which can only be accessed by the investigators and staff. All surveys and assessments will be under the direction of the Investigators who will supervise Research Assistants. Recruitment, screening, and project implementation will be coordinated by the Investigators and/or research staff. The data management group, supported by the IT department of the College of Public Health and Health Professions, will manage the database, monitor subject recruitment and distribute monthly enrollment reports, and produce reports summarizing the status of data acquisition, the baseline characteristics and the blinded primary variables. The database mentioned above is the storage place for all participants who call and wish to be pre-screened for the study. In many instances, the prospective participant no longer wants to enroll in the study, once they learn of the time commitment and details involved in participating.

Data Sharing with Collaborating Site: With permission of participants, de-identified data will be shared between the University of Florida and the collaborating site, the University of Arizona. De-identified questionnaire, cognitive, mood, and other data will be stored via the secured infrastructure of the University of Florida REDCap System. De-identified raw neuroimaging data will be transferred using Secure File Transfer Protocol (SFTP) onto UF Dropbox servers.

13. Possible Discomforts and Risks

The risks are minimal for individuals who participate in this study. Light is applied using light emitting diodes, which do not present as a serious ocular hazard. Near infrared light is non-thermal, painless, and is designated as a non-significant risk. It is estimated that approximately 6 J/cm^2 is expected to reach the cortex with each daily treatment. At this energy level, the MedX system and/or the

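### The plan does not conceal the next assignment from staff who screen and enrol, and describes the allocation method in conflicting terms with no stated random element

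*Protocol*

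**What the plan says.** Protocol section 8.2a is the main description of how treatment is assigned. It makes three statements in a row:

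- "Participants will be independently assigned to Sham and Active groups on a 1:1 ratio"
- "Randomization will be stratified according to age and MoCA scores"
- "Treatment assignment will be pseudorandomized in order to have comparable distributions of age and cognitive screening scores across Sham and Treatment interventions"

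It gives no cut-points, block size, random element or sequence holder. Section 7.2 repeats the 1:1 ratio but lists other factors ("stratified by age, education, and gender"). The SAP does not describe allocation.

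On who is kept unaware, section 8.2a says that procedures will ensure that "group assignments are not available to individuals administering and scoring baseline/pre-intervention and post-intervention cognitive/mood data". Section 7.6.3 adds that the assistant for testing and image acquisition is blinded, and it provides sham devices. It also states: "The research assistant administering the lab stimulation session will be aware of the participant's treatment status". That assistant is excluded from pre- and post-intervention assessments and from nothing else.

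On enrolment, section 12 says: "Recruitment, screening, and project implementation will be coordinated by the Investigators and/or research staff". The consent text in section 7.2 has the study coordinator or approved staff explain the study and review consent. Section 14 has the study coordinator apply the diodes.

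**The concern.** Two things are missing, and the second matters more.

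First, the method is unclear. If assignments are chosen to make the groups alike on age and screening scores, each may depend on those before it. That sits badly with calling them independent, and the reader cannot tell how much chance remains.

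Second, the safeguards described protect outcome measurement and participant masking. None protects the moment of entry. Age and MoCA are known at screening, before assignment. Section 7.5 places baseline testing and randomisation in the same step without a firm order, and section 9 allows baseline testing to be spread over several days. Anyone who could anticipate the next assignment would have room to bring a participant forward or hold one back.

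Steering of that kind could favour one arm on features that nobody records. Tables of age and MoCA would still look balanced, and adjusting for baseline would remove only the part that the covariates carry. The test of β in SAP equation (1), the primary comparison, relies on assignment being unrelated to prognosis.

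**Working it through.** **1. Who is kept from knowing what**

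| Group | Protection stated | Does it hide the next assignment at entry? |
|---|---|---|
| Testers and scorers (8.2a) | Assignments withheld | Only if the same people also enrol, which is not stated |
| Imaging acquisition (7.6.3) | Blinded | No |
| Participants (7.6.3) | Sham devices | No |
| Session assistant (7.6.3) | None; knows the status of those treated | No; barred from assessments only |
| Staff who screen, consent or schedule (7.2, 12) | None stated | No |

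**2. Predictability under assumed schemes**

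The plan has no figure for this and no algorithm, so these values illustrate and do not estimate.

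From the documents: 168 participants, half at each of two sites, 1:1 ratio, age and MoCA as balancing factors. Assumed: each factor is binary with equal halves, allocation runs within site, and the guesser knows every earlier assignment at the site and picks the arm that is behind. Each scheme was simulated for at least 300 trials.

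| Scheme | Next assignment guessed correctly |
|---|---|
| Simple randomisation | 50% |
| Stratified blocks of varying size (sets from 4/6/8 to 2/4) | 67 to 71% |
| Stratified blocks of fixed size 6, 4, 2 | 67%, 70%, 75% |
| Minimisation with a 0.8 biased coin | 74% |
| Deterministic minimisation | 86% |

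Under deterministic minimisation about 72% of assignments are fully fixed in advance.

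The result depends strongly on complete knowledge. If the guesser misses a random 10% of earlier assignments, deterministic minimisation falls to 66% and the biased coin to about 63%. At 25% missed, they fall to 60% and 59%.

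**3. What foresight could do to the primary test**

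Suppose entry is steered by ±δ SD of prognosis that the covariates do not capture, and the guess is right with probability p. The expected prognosis is δ(2p − 1) in one arm and −δ(2p − 1) in the other, so the bias is 2δ(2p − 1). Take δ = 0.1 (assumption).

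The SAP's 15% attrition leaves 84 × 0.85 ≈ 71 per arm, so the standard error is √(2/71) = 0.168 SD. The two-sided 5% error rate becomes Φ(−1.96 + z) + Φ(−1.96 − z), with z = bias/0.168.

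| p | Bias (SD) | Error rate |
|---|---|---|
| 0.86 | 2 × 0.1 × 0.72 = 0.144 | 14% |
| 0.74 | 2 × 0.1 × 0.48 = 0.096 | 9% |
| 0.67 | 2 × 0.1 × 0.34 = 0.068 | 7% |
| 0.50 | 0 | 5% |

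**4. Are the balancing factors in the model?**

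Section 8.2a balances on age and MoCA. The SAP adjusts for the baseline outcome, age, sex, education and further confounders listed under Aim 3. MoCA is not named among them.

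**The case against.** The best reply is that this is loose wording about an ordinary scheme. A computer-generated restricted list is both stratified and, in a common sense, pseudorandom. The sentence on comparable distributions may only restate the aim of stratifying, and independence may be meant informally. That stands: a reader might infer that section 8.2a sets out mutually exclusive methods, or that the next assignment follows a running tally, but the text gives an aim and no mechanism.

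A reader might also infer that session staff know all past assignments. Section 7.6.3 says only that the assistant knows the status of the participant being treated, and there are two sites. The shared coordinator title is weak evidence of overlapping roles, because section 14 uses it loosely and also places the coordinator in cognitive testing. Section 12 does not say that unblinded staff enrol.

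There are real mitigations. Session staff do not run the baseline tests, eligibility is narrow, and the model adjusts for the baseline outcome, age, sex and education. Finally, a change of algorithm gains little by itself: with full knowledge, varying blocks are guessed almost as often as a biased coin.

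What remains is that neither document conceals the next assignment from those who control entry, or bars staff who know assignments from that work. None of the mitigations closes that gap.

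**Conclusion.** The concern holds as a risk left open. The documents do not show that anyone could in fact foresee assignments, still less that anyone did.

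The size cannot be fixed without the algorithm. With full knowledge of earlier assignments at a site, the restricted schemes tried give 67 to 86% correct guesses, against 50% for simple randomisation. The 86% figure needs both a deterministic rule and a complete tally, and the documents support neither, so it should not be read as this trial's predictability. The 7 to 14% error rates also assume deliberate steering by 0.1 SD.

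The plan should be changed because the validity of the primary comparison rests on a step that is neither defined nor concealed, and closing the gap is cheap. It is separate from the conflict over stratification factors between sections 7.2 and 8.2a, which needs its own reconciliation.

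**What to change.** In Protocol section 8.2a:

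1. Replace the two conflicting descriptions (independent, pseudorandomised) with one computer-generated stratified scheme that has a stated random element, such as permuted blocks of varying size within the final strata.
2. Hold the sequence centrally, for example in REDCap, which the trial already uses. Release each assignment only after eligibility and baseline testing are complete, and only to the session assistant.
3. Bar anyone who knows assignments from screening, consent and decisions on the order of entry. This and the concealed release give most of the protection.

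In the SAP, add the balancing factors actually used, including MoCA, to equations (1) and (2).

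If allocation has already taken place, report the algorithm that was used and who could see assignments, and fit its balancing factors.

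The cost is protocol and SAP wording, REDCap set-up, slightly less exact balance on age and MoCA than forced matching would give, and some separation of session staff from enrolling staff at each site. The sample size does not change.
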